EXCLUSION CRITERIA: (A1) not currently working as a Frontline Health Worker/Health Facility Manager at a participating study facility or (A2) not currently working as a District Health Supervisor in a participating district or (A3) not currently working in Mozambique in the clinical delivery of HIV and/or hypertension care and treatment or (B1) HIV-negative or of unknown status or <18 years old or age not recorded, or or pregnant or postpartum.

NUMBER OF SUBJECTS:

Group name/description	Maximum desired number of individuals (or other subject unit, such as families) who will complete the research *For clinical trials: provide numbers for your site and for the study-wide total number
Frontline Health Workers (FGD)	224
Frontline Health Workers (ORIC)	70
Health Facility Managers (IDI)	48
Health Facility Managers (ORIC)	12
District Health Supervisors (IDI)	24
Provincial Health Experts	4
Frontline Health Workers (Costing)	30

RESEARCH SETTING: The SAIA study includes 16 public sector facilities, 8 of which will receive the SAIA intervention in outpatient, emergency and related (pharmacy, etc) services where HIV care and treatment is currently mainstreamed into primary healthcare services in Manica and Sofala provinces in Mozambique. Manica and Sofala provinces (population ~4 million, HIV prevalence 15.3% and 15.5%, respectively) were selected because of the deep relationship between investigators and health authorities, and absence of structural interventions for HTN diagnosis and management (both within HIV care and general outpatient services).

LOCAL CONTEXT: In the study area (central Mozambique), over 98% of formal health services are offered through the public sector, and primary care utilization is high, supporting spread and likelihood of population-level impact for a supply-side intervention delivered through the HIV treatment platform.

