OUTCOME DEFINITION: The study has two primary endpoints. The first is a process outcome and measures the activation of the hypertension care cascade – the proportion of ambulatory care consults for PLHIV at which blood pressure was screened. The second is a patient level clinical outcome – the proportion of clients eligible for hypertensive medication who attain blood pressure control. Hypertension medication eligibility was guided by a simplified risk stratification tool, but ultimately established by clinicians. This tool describes eligibility as an additive risk score of at least 3 according to the following parameters: 1) score of three for PLHIV previously on or presently initiating hypertensive medication and/or with blood pressure of at least 160/100 mmHg; score of two for blood pressure between 140/90 mmHg and 160/100 mmHg, score 1 for the presence of any number of non-modifiable risk factors (such as previous Myocardial Infarction, Coronary Vascular Disease and Diabetes Mellitus); and score of 0.33 for any number of modifiable risk factor (such as smoking, overweight, and sedentarism). Controlled hypertension is defined as blood pressure reading of ≤140/90 mmHg in clients with verified hypertension. Between these two endpoints, we also assess the proportion of patients that successfully progress from being screened, to treatment eligible, to receiving a prescription, to accessing the prescribed medication and to attaining blood pressure control.

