SAMPLE SIZE AND RANDOMIZATION: Sample size estimation was based on the anticipated absolute difference in the proportion of ambulatory care consults at which hypertension is screened during the last three months of using the SAIA-HTN implementation strategy. Hypertension screening was selected because it is the first step of the hypertension care cascade and its routine use in outpatient visits is recommended by existing guidelines. In the pilot study leading up to this trial, the proportion of ambulatory care consults at which hypertension was screened at the beginning of the pilot was less than 10%, and a 31% increase was observed at the end of the pilot. Assuming an $\alpha = 0.05$ and 1000 HIV care outpatient visits over each 3-month period, we estimated that eight intervention and eight control clusters would be sufficient to have 80% power to detect an absolute difference in the outcome of between 15 and 29%, depending on plausible values of the effect size in the control sites (i.e. 10 to 20% of care consults at which hypertension screening was done) and intra-cluster correlation between 5 and 15%. To select the eight intervention and control clusters, 29 eligible health facilities across the two provinces were stratified by province (Manica or Sofala) and by type (urban or peri-urban) and 1:1 randomized to either intervention or control arm within each stratum, so that two urban and two peri-urban health facilities were allocated for each arm, in each province. Adult (>18 y/o) clients were automatically assigned to either intervention or control arms in dependence of the respective cluster where they access ambulatory care consults.

ANALYSIS APPROACH:

Descriptive analysis

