We described health facility characteristics at baseline and the study participant population both during baseline, and at the time of recruitment for each study phase, in terms of sex, age and hypertension care outcomes status. For the primary process outcome, we describe the number and proportion of outpatient consultations at which blood pressure was screened in each study phase. To describe the hypertension care cascade, we ascertain the proportion of patients who, within the phase they are recruited, are ever screened and diagnosed as eligible for hypertensive treatment, ever receive a prescription and pick-up the medication prescribed, and who present controlled blood pressure control in the last two ambulatory consultations (if same outcome observed in both visits) or in most consultations. Ambulatory consultations beyond the phase of recruitment are censored.

Inferential analysis

To assess the effect of SAIA-HTN, we ascertained clinical outcomes in all ambulatory care visits within each phase (observations attributed to the phase in which consultations took place), and estimated the population level risk of the outcomes using Generalized Estimation Equations (GEE) and Log-binomial or Poisson regressions, assuming an exchangeable correlation structure to account for clustering at the level of health clinic, and adjusted for study phase and for whether patients were newly recruited or retained from a prior study phase (Model 1).

Model 1: $log(E[yij]) = \beta_0 + \beta_1 \cdot x_{ij} + \beta_2 \cdot phase_{ij} + \beta_2 \cdot recruitment_{ij} + u_{ij}$

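### Model 1 leaves out client age and sex, so any difference in their mix between arms stays in the blood pressure control ratio; an age- and sex-adjusted ratio should be reported beside it

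*Combined protocol and SAP*

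**What the plan says.** Under ANALYSIS APPROACH, Inferential analysis, the plan fits a GEE with an exchangeable correlation by clinic, log-binomial or Poisson, "adjusted for study phase and for whether patients were newly recruited or retained from a prior study phase (Model 1". The printed equation has an arm term, a phase term and a recruitment term, and no others. The supplied text ends at that equation.

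Under Descriptive analysis, clients are described at baseline and "at the time of recruitment for each study phase, in terms of sex, age and hypertension care outcomes status", so age and sex are in the data set. EXCLUSION CRITERIA removes clients who are "HIV-negative or of unknown status or <18 years old or age not recorded", which makes age complete by design. Nothing is said about the completeness of sex, and no reason is given for leaving either variable out.

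Under OUTCOME DEFINITION, the second primary endpoint is "the proportion of clients eligible for hypertensive medication who attain blood pressure control". On who enters that denominator: "Hypertension medication eligibility was guided by a simplified risk stratification tool, but ultimately established by clinicians".

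**The concern.** Sixteen clinics were randomised within province and urban/peri-urban strata. That does not balance the age and sex of the clients who attend, and both could be related to blood pressure control.

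The control ratio has a second route to imbalance. Its denominator contains only clients found eligible for medication. They are found through screening and clinician judgement, and screening is the first step of the cascade that the intervention sets out to improve. SAIA cannot change a client's age or sex, but it can change which ages and sexes reach the denominator. Whichever route produces the difference, Model 1 leaves it in the arm ratio for a primary endpoint. The plan already accepts client-level adjustment, since it uses new-versus-retained status, so age and sex would not be a change of principle.

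**Working it through.** **1. The plan's only design figure.** It concerns screening: "eight intervention and eight control clusters would be sufficient to have 80% power" for an absolute difference of 15 to 29 points, with control proportions of 10–20% and ICC 0.05–0.15. I took the effective number per arm as 8m/(1 + (m − 1) × ICC), two-sided alpha 0.05 and 80% power.

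- 1000 visits per clinic (m = 1000): 11.5 to 25.2 points.
- 1000 visits in total (m = 1000/16 = 62.5): 13.3 to 26.4 points.
- The same with a continuity correction: 14.3 to 28.9 points.

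The stated range is approached but not reproduced, perhaps because of unstated settings. Nothing below depends on it. There is no design figure for blood pressure control.

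**2. Assumed inputs.** None of these is in the documents: SD of clinic mean age 1–4 years; absolute log ratio for control per 10 years of age 0.05–0.3; SD of the clinic share of men 5–10 points; sex ratio 0.8–0.9; control 30–50%. The ICC of 0.05–0.15 is borrowed from screening. Because allocation was stratified, the relevant SD is the one within strata.

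**3. Chance age gap between arms.** SD of the gap = s × sqrt(2/8) = 0.5s, so the 95% limit is 1.96 × 0.5 × s. This gives 2.0, 2.9 and 3.9 years for s = 2, 3 and 4.

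**4. Shift in the control ratio at that limit**, with a ratio of 0.8–0.9 per 10 years:

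- 0.9^0.20 = 0.98 (2%)
- 0.8^0.29 = 0.94 (6%)
- 0.8^0.39 = 0.92 (8%)

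**5. The same as a one-SD shift**, |log ratio per 10 years| × (s/10) × 0.5:

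| s (years) | log ratio per 10 years | SD of shift in log ratio |
|---|---|---|
| 1 | 0.05 | 0.0025 |
| 2 | 0.1 | 0.010 |
| 4 | 0.1 | 0.020 |
| 4 | 0.3 | 0.060 |

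The middle rows are the typical 1–2%. The last row has a 95% limit of 1.96 × 0.060 = 0.118, somewhat beyond 8%. Sex adds little: |ln 0.9| × 0.05 × 0.5 = 0.003 up to |ln 0.8| × 0.10 × 0.5 = 0.011. These formulas cover chance only; a difference produced by selection is not bounded by them.

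**6. Compared with the standard error.** SE(log ratio) = sqrt(ICC(1 − p)/p) × sqrt(2/8). It runs from 0.11 (p = 0.5, ICC 0.05) to 0.30 (p = 0.3, ICC 0.15). The typical shift is small beside it.

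**7. Precision, by simulation** (Poisson GEE, exchangeable, 16 clinics). SD of the log ratio without and then with adjustment:

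- 60 clients per clinic, 1000 runs per setting, age and sex: moderate association 0.166 to 0.164 (ICC 0.05) and 0.249 to 0.244 (ICC 0.15); strong association with wide spread 0.172 to 0.153, about 11% smaller; no association 0.166 to 0.166.
- 120 clients per clinic, 150 runs per setting: 0.137 to 0.139, 0.137 to 0.136, and 0.121 to 0.115. An SD from 150 runs has a Monte Carlo error near 6%, since 1/sqrt(2 × 150) = 0.058. Pairing makes the comparison tighter than that, but the smallest changes should not be over-read.

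In the 1000-run settings the adjusted and unadjusted log ratios differed with SD 0.020, 0.044 and 0.074 where there was an association (in the order listed), and 0.008 where there was none. Some of that movement is therefore noise from estimating the extra coefficients, not removed imbalance.

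**8. Price.** If two between-clinic degrees of freedom are charged, the critical t goes from 2.145 (14 df) to 2.179 (12 df), and 2.179/2.145 = 1.016, or about 1.6% wider intervals.

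**The case against.** The strongest reply is that no error has been shown. Clinics were randomised, so chance imbalance is not bias, and a valid clinic-level interval already allows for it. That stands: against chance imbalance, the benefit is precision and credibility of the particular estimate obtained. It does not cover imbalance from selection into the denominator, which randomisation of clinics does not protect against.

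A reader might infer that adjustment is free. The documents do not support that. Completeness is assured for age only, a log-binomial fit with continuous age may not converge, degrees of freedom may be lost, and in one simulated setting precision was slightly worse.

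A reader might also infer that, because a risk ratio is collapsible, the arm coefficient keeps its meaning. That is not secure here. When composition differs by arm, or the effect varies with age, the adjusted ratio is standardised for composition and need not equal the ratio from Model 1. Nor does adjustment remove the selection problem; it takes out only the part that runs through age and sex.

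Timing also counts. The document is dated 10/23/24 and PROCEDURES places trial conduct between 2019 and 2023, so covariates added now are post hoc unless an earlier specification exists.

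Finally, the absence of province and clinic type from Model 1, and of any small-sample correction for 16 clusters, matters more. In the 1000-run simulations the uncorrected z test rejected in 10–11% of trials with no effect, with or without age and sex. This sets the priority but does not answer the point, and one edit can deal with all three.

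**Conclusion.** The point holds as a low-cost improvement. Model 1 as printed omits two recorded client characteristics, one complete by design, and any difference between arms in their mix stays in the blood pressure control ratio. On assumed spreads and associations the chance shift is typically 1–2%, and about 8% or somewhat more at the extreme, against a clinic-level SE of 0.11–0.30 on the log scale. The effect on the SD of the log ratio ranges from about 1% larger to about 11% smaller.

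Two limits apply. All of these sizes rest on inputs that the documents do not give. And since the supplied text stops at Model 1, a further adjusted model cannot be ruled out. The documents do not support saying that Model 1 is biased by chance imbalance, or that age and sex terms would make the eligible groups comparable.

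**What to change.** For blood pressure control and for the eligibility step, fit Model 1 with age (continuous, with a quadratic term or spline) and sex added. Use Poisson with robust standard errors if log-binomial does not converge; the plan already allows Poisson. Report the ratio beside the one without these terms, so that the reader sees how much of the result runs through age and sex. State when the adjusted model was specified, and label it a post hoc sensitivity analysis unless that was before the data were seen. State how many records lack sex and how they are handled. Say in the text that the adjusted ratio is standardised for age and sex composition and does not correct for post-randomisation selection into the eligible group.

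The cost is a few sentences of SAP wording and covariates already collected. The downsides are intervals about 1.6% wider if two degrees of freedom are charged, and possible loss of records with missing sex. The stratification terms and a small-sample correction can go into the same edit.

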clinical experts, and 24 in-depth interviews (IDIs) with key informants (frontline health workers and managers), to assess feasibility and refine the SAIA-HTN strategy. Critical HTN cascade steps were identified, and the HTN Cascade Analysis Tool (HCAT) developed. Data sources were mapped, and a registry to populate the HCAT and capture relevant study outcomes from outpatient registries and patient charts was developed. Clinical pathways and tasks were described in outpatient and emergency services, where both HIV and HTN screening and care is provided by both mid- and higher-level providers at the health center level, with complicated cases referred to reference hospitals. Mid-level providers may initiate HTN medications under supervision of a higher-level provider, while both mid- and higher-level providers may prescribe anti-retrovirals. SAIA-HTN was piloted in one facility and after twelve weeks of implementation, HTN screening improved 4-fold. In FGDs and IDIs, frontline health workers and managers were enthusiastic about SAIA-HTN and found the focus on HTN relevant and timely. Through other research in the study area (R01HD075057, R01MH113435, and R01HD092449), we have translated and adapted the CFIR tools for the local setting, and trained study personnel on their application. Stakeholder meetings have also been held with national, provincial and district authorities to seek consensus on the SAIA-HTN and trial design, including study location.

PARTICIPANTS: Health Facility Managers, District Health supervisors and leading cardiovascular and HIV Clinical Experts (medical doctors or nurses) at the sub-national level (provincial, district) will participate in in-depth individual interviews. A small number of providers will also be recruited to complete a recall survey on the amount of time they spend dedicated to hypertension care which will inform the costing analysis. There will be no direct contact with patients, as the SAIA-HTN intervention only involves periodic engagement with health workers. Regularly collected, de-identified clinical outcomes related to controlled hypertension and process outcomes related to blood pressure screening, anti-hypertension medication initiation and maintenance in care will be obtained as part of the study.

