There are two groups of human subjects involved in this project. The first group are patients ≥18 years old accessing services at the 16 facilities, eight of which will be implementing the Systems Analysis and Improvement Approach (hereafter referred to as patient subjects). Over the course of the study, we expect that the number of patient subjects attending HIV care and linked hypertension screening, care and treatment services will number in the thousands. Using de-identified, routine health system records, we will be measuring outcomes that reflect more consistent implementation of Ministry of Health norms (including blood pressure screening, treatment initiation and maintenance in care for hypertension as well as monitoring controlled hypertension). We expect the sample to be approximately half male and half female, given that HIV services are typically gender-balanced in the study setting.

The second group of human subjects involved in this study are Frontline Health Workers and Health Facility Managers working in outpatient and HIV services, and District Health Supervisors and Clinical Experts who will support dissemination of the study intervention. We expect Frontline Health Workers, Health Facility Managers, District Health Supervisors and Clinical Experts to be approximately half male and half female, aged 18-65 years. These participants will be recruited and asked to consent to participate in FGDs, individual interviews, or an end-of-day recall survey to estimate time spent on hypertension-related tasks. Participants recruited are free to decline to enroll or to decline to continue participation with no adverse consequences to their employment.

INCLUSION CRITERIA: (A1) Frontline Health Workers / Health Facility Managers currently working in outpatient and HIV services at one of the study clinics in Manica and Sofala provinces, Mozambique; (A2) District Health Supervisors currently employed in a study district in Manica and Sofala provinces, Mozambique regularly engaged in service provision or management of HIV-infected and/or hypertensive populations; and (A3) Clinical Experts currently working in Mozambique in the clinical delivery of HIV and/or hypertension care and treatment *or* (B1) PLHIV ≥18 years old who also access HIV care and treatment services via outpatient services in study clinics.

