evaluate SAIA-HTN effectiveness on HTN cascade optimization (Aim 1); identify its drivers of implementation success (Aim 2); and determine costs and cost effectiveness on HTN and HIV performance measures (Aim 3). The SAIA-HTN trial was conducted in eight intervention and eight control health clinics, between 2019 and 2023 and over three phases: (1) a 3-month preparatory phase, which included the baseline period from July to September 2020, (2) a 24-month intensive implementation phase in which implementation was supported by the research team, and (3) a 12-month sustainment phase where research team support is removed in Manica and Sofala provinces in central Mozambique. District Health Supervisors, supported by study nurses, will deliver the intervention during the intensive phase, followed by a one-year sustainment phase led by the District Health Supervisors without additional study personnel support. In all 16 health clinics, government health workers provided hypertension care to clients accessing HIV services. Clinician training included a refresher on Mozambique Ministry of Health guidelines on clinical management of hypertension and the use of hypertension treatment job-aids. Both clinicians and data clerks received phone credit vouchers as incentives for the additional work of data collection for the purpose of the study. Sphygmomanometers were allocated to every consultation room where clinicians provided outpatient/HIV services to allow for similar opportunity for hypertension screening in all sites. From July 2020, all 16 sites began to use study data collection tools to collect patient level hypertension care data at every ambulatory care visit, for both new and returning clients. The frequency and schedule of ambulatory consultations was not uniform across clients.

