In eight health clinics assigned to the intervention arm, SAIA-HTN implementation started in October 2020. SAIA is composed of four components – (1) the Hypertension Cascade Analysis Tool – HCAT, (2) Process Mapping, (3) Continuous Quality Improvement – CQI, all of which are operationalized during (4) monthly SAIA meetings. The HCAT uses health facility aggregate patient data to assess the flow of patients through the care cascade, indicate where in the cascade major drop-offs occur, and indicate at which step improvements may result in more patients achieving controlled hypertension. Process mapping consists of a health worker joint assessment of patient paths through hypertension services within the health facility to identify inefficiencies and inconsistencies that may be addressed for improvement. The CQI consists of Plan, Do, Study, Act monthly cycles, in which implementers define a problem based on findings of the hypertension care cascade assessment and process mapping, define and implement solutions to address the defined problem, and iteratively assess the effect of the solutions implemented by reassessing the performance of the hypertension care cascade, reviewing the process map, and sharing anecdotal experiences together. Depending on the perceived feasibility and effectiveness of the solutions implemented during the month, implementers decide if solutions are to be abandoned, adapted for further testing, or adopted as a practice that is to be continued.

The mixed-methods evaluation will evaluate the impact of SAIA-HTN on clinical (controlled HTN, HIV viral load suppressed) as well as process (BP screened, HTN diagnosis, HTN medications prescribed, HTN medications picked up) outcomes. The consolidated framework for implementation research (CFIR) will be used to guide data collection and interpretation related to implementation, to assess fidelity to intervention protocol, describe intervention adaptations when integrated into routine management systems, and identify organizational-level determinants of successful SAIA-HTN implementation. Based on trial results, we will model out the costs and potential benefits on HTN control given different scale-up scenarios within Mozambique. The trial will culminate in a dissemination package, summarizing trial results and providing implementation and cost guidance to support national SAIA-HTN scale-up.

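### In the sustainment phase, Model 1 adjusts for newly recruited versus retained status, which SAIA-HTN can itself change, so the adjusted risk ratio may differ from the total effect of assignment.

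*Combined protocol and SAP*

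**What the plan says.** Under ANALYSIS APPROACH, Inferential analysis, the plan fits a GEE log-binomial or Poisson model to all ambulatory visits, with clustering by clinic, adjusting for phase and for "whether patients were newly recruited or retained from a prior study phase" (Model 1). Visits enter by date: "observations attributed to the phase in which consultations took place". No other inferential model is shown. The plan gives no reason for the recruitment term and no version without it, and it does not plan to report the retained share by arm.

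Three other places bear on how that term should be read.

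- **Timing (PROCEDURES).** The preparatory phase contains "the baseline period from July to September 2020", and "SAIA-HTN implementation started in October 2020". Then come "a 24-month intensive implementation phase" and a 12-month sustainment phase.
- **Staying in care as an outcome (PARTICIPANTS).** The data to be obtained include "process outcomes related to blood pressure screening, anti-hypertension medication initiation and maintenance in care". The same section later names "treatment initiation and maintenance in care for hypertension" among the measures expected to reflect better implementation.
- **Primary endpoints (OUTCOME DEFINITION).** The first is the proportion of consultations for people living with HIV at which blood pressure was screened. The second is the proportion of medication-eligible clients who attain blood pressure control.

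**The concern.** Randomisation of clinics protects a comparison of everything that follows assignment. Adjusting for a variable measured after assignment, which assignment can alter, holds part of what follows fixed. If SAIA-HTN keeps more clients in hypertension care, and those clients have had longer to be diagnosed, treated and controlled, some of the benefit passes through retained status and the adjusted coefficient leaves it out. If retained clients do worse instead, adjustment raises the estimate.

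The stated purpose of the model is to assess the effect of SAIA-HTN, and the first primary endpoint is a proportion over all consultations. Neither is defined within strata of client history. The risk is that the headline risk ratio answers a different question from the one the randomisation was set up to answer, with nothing reported that would let a reader see the gap.

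**Working it through.** The plan gives no figure for the retained share or for the association of status with outcome, so there is nothing of its own to reproduce on this point. Its detectable difference of 15 to 29 percentage points (SAMPLE SIZE AND RANDOMIZATION) does not involve the recruitment term and serves only for scale.

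**Step 1. When is the status fixed?**

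| Phase | Retained means | Can SAIA-HTN change it? |
|---|---|---|
| Baseline, July to September 2020 | No earlier study phase exists | No |
| Intensive, 24 months from October 2020 | First seen July to September 2020 | Not who they are; only whether and how often they return |
| Sustainment, following 12 months | First seen at baseline or during the intensive phase | Yes: includes clients first seen or kept under the intervention |

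The problem of status itself is therefore confined to the sustainment phase. In the intensive phase only the mix of visits can shift. PROCEDURES says that visit frequency varied between clients.

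**Step 2. Illustration with no effect within either type of client.** All inputs are assumed: the retained share of visits is 60% in control and 75% in intervention; screening is 30% at retained clients' visits and 15% at new clients' visits, in both arms.

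- Control: 0.40 × 0.15 + 0.60 × 0.30 = 0.2400
- Intervention: 0.25 × 0.15 + 0.75 × 0.30 = 0.2625
- Total risk ratio: 0.2625 / 0.2400 = 1.09
- Adjusted risk ratio: 0.30 / 0.30 = 0.15 / 0.15 = 1.00
- Absolute shift: 26.25% − 24.00% = 2.25 points

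**Step 3. Range when there is also an effect within each type of client.** Assume a within-status risk ratio of 1.50 and a control retained share s0 = 0.50. Let s1 be the intervention retained share and g the risk ratio for the outcome, retained versus new. Then

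total RR = 1.50 × (1 − s1 + s1·g) / (1 − s0 + s0·g),

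and the adjusted RR is 1.50 throughout.

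| g | s1 = 0.50 | s1 = 0.60 | s1 = 0.70 |
|---|---|---|---|
| 0.7 | 1.50 | 1.45 | 1.39 |
| 1.0 | 1.50 | 1.50 | 1.50 |
| 1.2 | 1.50 | 1.53 | 1.55 |
| 1.5 | 1.50 | 1.56 | 1.62 |
| 2.0 | 1.50 | 1.60 | 1.70 |

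For example, with g = 1.5 and s1 = 0.60: 1.50 × (0.40 + 0.90) / (0.50 + 0.75) = 1.50 × 1.30 / 1.25 = 1.56. With no arm difference in share, or no association (g = 1), the term changes nothing. With g above 1 adjustment lowers the estimate; with g below 1 it raises it.

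These are comparisons of expected proportions within one phase, ignoring clustering. How far a shift in sustainment carries into Model 1's arm coefficient also depends on the share of visits in that phase, which the plan does not give.

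**Step 4. Does dropping the term cure selection through attendance?** Assume 100 earlier clients per arm, half of them engaged. Engaged clients return at 80% in both arms and are screened at 40% of visits. Less-engaged clients return at 40% in control and 60% in intervention, and are screened at 20%. Each client who attends makes one visit. Add 20 new clients per arm, screened at 30%. There is no effect on screening within any client type.

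- Control: 40 engaged + 20 less engaged + 20 new; screened 16 + 4 + 6 = 26 of 80 = 0.3250
- Intervention: 40 + 30 + 20; screened 16 + 6 + 6 = 28 of 90 = 0.3111
- Without the term: 0.3111 / 0.3250 = 0.957
- With the term (Poisson log-link fit to the same cells): 0.955

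Clients who leave make no visits, so they are missing from both analyses. Dropping the term makes almost no difference to this selection.

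**The case against.** Several points can fairly be made for the plan as written.

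- **For most of follow-up the covariate predates the intervention.** This stands. In the 24 intensive months it is the same variable as the fixed July to September 2020 indicator suggested below. If shifting visit mix is the worry, that indicator shares it.
- **The outcome listed is maintenance in hypertension care, while the covariate covers attendance by any adult with HIV.** This stands in part. One of the two mentions is specific to hypertension, and the outcome list in PROCEDURES has no retention outcome. The documents do not say that SAIA-HTN should change general HIV attendance. The pathway is most plausible among clients in hypertension care, and so for the blood pressure control endpoint.
- **A change in visit mix may not count as an effect.** The plan defines no estimand that settles this. That is a reason to show both versions. It does not justify making the conditional one the only one.
- **The illustrated shift is small.** It is 2.25 points against a design for 15 to 29, and its inputs are assumed.
- **The analysis may already have been done.** The document is dated 10/23/24 and describes model fitting in the past tense, so a new primary model would be a late change. This stands and shapes the remedy.

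A reader might go further and infer that adjustment certainly removes part of the benefit, or that it creates a selection bias which dropping the term would cure. The documents support neither. The first needs both an arm difference in retained share and an association with outcome, and neither is given; the sign can go either way. The second fails on the arithmetic: selection through who attends is present with or without the term.

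**Conclusion.** The concern holds in limited form. In the sustainment phase Model 1 conditions on a post-randomisation variable that the intervention can change, and the plan gives neither a reason for this nor an unconditioned estimate. The consequence is conditional: the adjusted and total risk ratios differ only if the retained share differs by arm and status is related to outcome.

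The size is unknown. Under the assumed inputs, a total risk ratio of 1.09 becomes 1.00. With a within-status risk ratio of 1.50, an arm difference in retained share of 10 to 20 points and an association of 1.2 to 2.0, the total is 1.53 to 1.70 against 1.50 adjusted. With an association of 0.7 it is 1.39 to 1.45 against 1.50.

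This is a worthwhile, inexpensive improvement. It is not evidence that the trial's result is wrong.

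**What to change.** 1. In the primary model, drop the recruitment term, or replace it with one fixed indicator: seen at the clinic in July to September 2020, yes or no. The indicator differs from the present term mainly in sustainment.
2. Keep Model 1 as written as a sensitivity analysis.
3. Report the retained share of visits and the number of visits per client, by arm and phase. If these are balanced, the two models should agree. If they are not, the reader needs to see how far the result depends on the choice.
4. Because the analysis is described as already carried out, report both versions and label the change as made after the fact.
5. State that neither model removes selection through who continues to attend.

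The cost is one model term and one descriptive table. No new data are needed, since the present term already requires clients to be linked across phases. The downside is a possible small loss of precision.
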